##### **B- Exclusion criteria:**

- 1) Patients allergic to the used treatment
- 2) Patient receiving systemic steroids
- 3) Patients who don't approve to participating in the clinical trial.

#### **11. Interventions:**

**Enrolment:** Enrolment is expected to be done within a one-year period. The enrolled patients will be divided randomly into two groups, each consisting of 33 patients.

**Intervention group:** Patients will receive mixture of MEBO three times daily for 14 days

**Control Group:** Patients will receive Benzydamine Hydrochloride spray three times daily for 14 days.

**Follow up:** The patients will be recalled at one week interval for 14 days.

### **Criteria for discontinuing intervention:**

Occurrence of any harmful side effects from either of the treatment modalities.

### **Strategies to improve adherence to intervention:**

The patients will be recalled at one week interval and asked to bring the drug package.

## **12. Outcomes:**

Outcome measure		Method of measurement	Unit of measurement
1 st Outcome	Clinical improvement	World Health Organization (WHO)scale.(1)  Oral Mucositis Assessment Scale (OMAS).(2)	Numerical rating score
2 nd Outcome	Quality of life	Patient-Reported Oral Mucositis (PROMS questionnaire).(3)	Continuous outcome (Score codes).

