#### **10. Eligibility criteria:**

##### **A- Inclusion criteria:**

- 1) Patients having clinical signs of chemotherapy-induced or radiotherapy-induced OM (WHO oral mucositis grading scale: Grade II, III and IV)
- 2) Patients over the age of 18 years
- 3) Patients having no history of allergy, allergic rhinitis and asthma

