### ***Clinical parameters:***

#### **Clinical improvement of the lesion:**

The clinical data will be scored according to The World Health Organization (WHO)scale(1). It is graded from 0 to 4. If the patient has no signs and symptoms, it is graded as 0. If the patient has painless ulcers, edema, or mild soreness, it is graded as 1. If there is painful erythema, edema, or ulcers but able to eat, it is graded as 2. If there is painful erythema, edema, or ulcers but unable eat, it is graded as 3. If there a requirement for parenteral or enteral support, it is graded as 4

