#### **Quality of life**

The secondary outcomes will be quality of life assessed by PROMS scale.(2)

The PROMS scale consists of 10, 100-mm horizontal visual analogue scales addressing oral functions affected by oral mucositis. Participants will be asked to mark a point on the line that best represents their present intra-oral condition. During the baseline examination and prior to their completion of the actual PROMS scale questionnaire, participants were subjected to a few training test-visual analogue scale questions focused on simple everyday topics to familiarize them with the concept of visual analogue scale assisted measurements(19). The participants will

complete the PROMS questionnaire thrice; baseline, after the first week, and at the end of the study after the second week.

1. Mouth pain (Mouth encompass also lips, cheeks, tongue, gums, palate and throat)	
no pain	worst possible pain
_____	
2. Difficulty speaking because of mouth* sores	
no trouble	impossible to speak
speaking	
_____	
3. Restriction of speech because of mouth* sores	
no restriction	complete restriction of speech
of speech	
_____	
4. Difficulty eating hard foods (hard bread, potato chips etc) because of mouth* sores	
no trouble	impossible to eat hard foods
eating hard foods	
_____	
5. Difficulty eating soft foods (Jello, pudding etc) because of mouth* sores	
no trouble	impossible to eat soft foods
eating soft foods	
_____	
6. Restriction of eating because of mouth* sores	
no restriction	complete restriction of eating
eating	
_____	
7. Difficulty drinking because of mouth* sores	
no trouble	impossible to drink
drinking	
_____	
8. Restriction of drinking because of mouth* sores	
no restriction	complete restriction of drinking
drinking	
_____	
9. Difficulty swallowing because of mouth* sores	
not difficult to	impossible to swallow
swallow	
_____	
10. Change in taste	
no change in	complete change in taste
taste	

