### 13. Participant timeline

Enrolled patients will be divided randomly into two groups, each consists of 33patients.

**Intervention group:** Patients will receive mixture of Mebo and pumpkin seed oil spray three times daily

**Control Group:** Patients will receive Benzydamine Hydrochloride spray three times daily

**Follow up:** The patients will be recalled at one week interval for 14 days.

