## **20. Statistical methods:**

Data will be analyzed using IBM SPSS advanced statistics (Statistical Package for Social Sciences), version 21 (SPSS Inc., Chicago, IL). Descriptive statistics in case of normal distribution will be presented as mean and standard deviation, while if non-normal; median and 25th and 75th percentile will be used. Intergroup comparison will be done using t-test or Mann-Whitney test while Intra-group comparison will be done using student's t- test.

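### WHO and OMAS share the single primary outcome without a ranking; the text leans to WHO but fixes no primary visit, definition of improvement or multiplicity rule

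*Combined protocol and SAP*

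**What the plan says.** The PICO table and the table in section 12 each give one primary outcome, clinical improvement. Each lists two instruments in the same cell: the WHO scale and "Oral Mucositis Assessment Scale (OMAS).(2". Neither instrument is ranked. The tables differ on the unit: ordinal in the PICO table, a numerical rating score in section 12.

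Under the clinical parameters, the paragraph on improvement of the lesion describes WHO only: "The clinical data will be scored according to The World Health Organization (WHO)scale(1). It is graded from 0 to 4". WHO also sets eligibility ("WHO oral mucositis grading scale: Grade II, III and IV"). No section gives a scoring rule for OMAS.

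On timing, section 11 says "The patients will be recalled at one week interval for 14 days". Assessment times are written out only for the secondary outcome, where participants "complete the PROMS questionnaire thrice; baseline, after the first week, and at the end of the study after the second week".

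On analysis, section 20 says "Intergroup comparison will be done using t-test or Mann-Whitney test". It ties neither test to a scale or visit and has no multiplicity rule.

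Section 14 uses an effect size of 1.011 for a mean mucositis score, 80% power, 5% alpha and 1:1 allocation, and arrives at 17 per group. It does not name the scale or visit behind that score. Section 13 plans more patients: "Enrolled patients will be divided randomly into two groups, each consists of 33patients".

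**The concern.** A primary outcome has to lead to one answer. Here the plan leaves three things open: which scale decides, at which visit, and whether improvement is the grade reached or the change from baseline. If WHO and OMAS disagree, the plan cannot say whether MEBO gave clinical improvement. If the choice is left until the results are known, the more favourable scale or visit can be picked, and a nominal 5% test no longer has a 5% error rate. The sample size, by contrast, corresponds to one test at the full 5%.

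**Working it through.** **Inputs from the plan (section 14).** Effect size d = 1.011, alpha 5%, power 80%, allocation 1:1, stated result 17 per group. Planned enrolment is 33 per group (sections 11 and 13). Sidedness and type of test are not stated.

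**Step 1: reproduce the 17.**
- Normal approximation, two-sided: n = 2(1.960 + 0.842)² / 1.011² = 15.4, so 16 per group.
- Two-sample t-test, two-sided: 16.38, so 17 per group. This matches.
- Two-sample t-test, one-sided: 12.83, so 13 per group. This does not match.
- Mann-Whitney at efficiency 3/π (normal data): 16.38 / 0.955 = 17.15, so 18 per group.

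The stated figure therefore fits one two-sided t-test at 5%. That is an inference from the arithmetic, not something the plan says.

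**Step 2: false-positive chance if either scale counts.** Assume both scales are compared at day 14, each at two-sided 5%, with no true effect and test statistics that are bivariate normal with correlation r. The chance of at least one positive is 1 − P(|Z₁| < 1.96 and |Z₂| < 1.96). The plan gives no r, so a range is shown.

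| r | Either positive | Both positive (5% + 5% − either) |
|---|---|---|
| 0.9 | 7.0% | 3.0% |
| 0.7 | 8.3% | 1.7% |
| 0.5 | 9.1% | 0.9% |
| 0 | 1 − 0.95² = 9.75% | 0.25% |

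**Step 3: if both scales must succeed.** The error cannot exceed that of either single test, so it is at most 5%. The cost is power. Assume d = 1.011 on both scales.
- At 33 per group each t-test has power 98.1%. The joint power lies between 2 × 98.1% − 100% = 96.2% and 98.1%.
- At 17 per group each has 81.5%. The joint power lies between 2 × 81.5% − 100% = 63.0% and 81.5%.

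**Step 4: one named endpoint.** With one test at 5% and d = 1.011, power at 33 per group is 98.1% by t-test and 97.7% by Mann-Whitney at 95.5% efficiency. Simulated Mann-Whitney tests on a 0 to 4 grade, with ties and four assumed grade distributions, gave 97.6% to 99.5%.

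**The case against.** The strongest reply is that the plan already points to one endpoint. WHO is the only scale with scoring, it defines who may enter, and the quality-of-life paragraph treats week 2 as the end of the study. OMAS could then be a leftover entry in two tables. Much of this stands, and it is why WHO at day 14 is the natural choice. But neither the clinical parameters section nor section 20 makes WHO the sole primary measure, and both tables keep OMAS beside it. Even with WHO accepted, the visit and the meaning of improvement stay open.

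The second reply is that the inflation needs a success rule that the plan does not contain. That is correct. Requiring both scales is an equally open reading, and it does not inflate the error at all.

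Three stronger readings are tempting, and the documents do not support them.
- A reader might count four tests (two scales at two visits) and infer an error of about 9% to 16%. The plan does not say that WHO or OMAS is scored or tested at week 1.
- A reader might infer that the trial is underpowered. At 33 per group it is not, if d = 1.011 applies. The differing group sizes (17, 33, and 21 in the application form) are a separate matter.
- A reader might take the submission date of 12/9/2025 as proof that the data were already in hand. That date stands on an administrative page titled for a metformin trial in oral leukoplakia, so it should not be relied on. The planned January 2022 start in section 15, with "Enrolment is expected to be done within a one-year period", makes it possible that outcome data exist, but does not show it.

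Lack of blinding adds little here. It mainly threatens how outcomes are scored, while a late choice of scale is possible in any trial.

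**Conclusion.** The point holds as a gap in the definition of the primary endpoint. The plan lists two unranked scales for one primary outcome and names no primary visit, no definition of improvement and no multiplicity rule, although the text leans to WHO. The effect on the error rate is conditional: about 7.0% to 9.75% if both scales are tested at day 14 and either counts (assumed correlation 0.9 to 0), and at or below 5% if both are required. The documents do not settle which applies. The firm conclusion is therefore that scale and visit could be chosen after the data are seen, not that the trial's error rate has any particular inflated value. It should be corrected, and the correction is small.

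**What to change.** **Sections 12 and 20.** Name one primary endpoint: the WHO grade at day 14, the end of treatment, compared between groups at two-sided 5%. State that clinical improvement is judged by that comparison. Mann-Whitney is one suitable test and is already in section 20. An ordinal comparison adjusted for baseline WHO grade is an alternative, because patients enter at grades II to IV under simple randomisation (section 16a) and the groups may differ at baseline. Choose one of the two in advance. Make OMAS and any week-1 readings secondary.

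**Section 14.** State which scale and visit the effect size of 1.011 refers to. If it is not WHO at day 14, say so and restate the basis of the sample size.

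**Timing.** Record the date of the choice. If outcome data have already been seen, label the choice post hoc and report both scales at every visit scored.

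**Cost.** A few sentences, with no extra patients or visits. The price is that a difference on OMAS only, or at week 1 only, can no longer be claimed as primary success. If the choice has to be labelled post hoc, the result carries less weight.

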### ***Clinical parameters:***

#### **Clinical improvement of the lesion:**

The clinical data will be scored according to The World Health Organization (WHO)scale(1). It is graded from 0 to 4. If the patient has no signs and symptoms, it is graded as 0. If the patient has painless ulcers, edema, or mild soreness, it is graded as 1. If there is painful erythema, edema, or ulcers but able to eat, it is graded as 2. If there is painful erythema, edema, or ulcers but unable eat, it is graded as 3. If there a requirement for parenteral or enteral support, it is graded as 4

#### **Adverse Events**

Any adverse events and safety issues related to the administered drugs will be reported.

#### **Quality of life**

The secondary outcomes will be quality of life assessed by PROMS scale.(2)

The PROMS scale consists of 10, 100-mm horizontal visual analogue scales addressing oral functions affected by oral mucositis. Participants will be asked to mark a point on the line that best represents their present intra-oral condition. During the baseline examination and prior to their completion of the actual PROMS scale questionnaire, participants were subjected to a few training test-visual analogue scale questions focused on simple everyday topics to familiarize them with the concept of visual analogue scale assisted measurements(19). The participants will

complete the PROMS questionnaire thrice; baseline, after the first week, and at the end of the study after the second week.

1. Mouth pain (Mouth encompass also lips, cheeks, tongue, gums, palate and throat)	
no pain	worst possible pain
_____	
2. Difficulty speaking because of mouth* sores	
no trouble	impossible to speak
speaking	
_____	
3. Restriction of speech because of mouth* sores	
no restriction	complete restriction of speech
of speech	
_____	
4. Difficulty eating hard foods (hard bread, potato chips etc) because of mouth* sores	
no trouble	impossible to eat hard foods
eating hard foods	
_____	
5. Difficulty eating soft foods (Jello, pudding etc) because of mouth* sores	
no trouble	impossible to eat soft foods
eating soft foods	
_____	
6. Restriction of eating because of mouth* sores	
no restriction	complete restriction of eating
eating	
_____	
7. Difficulty drinking because of mouth* sores	
no trouble	impossible to drink
drinking	
_____	
8. Restriction of drinking because of mouth* sores	
no restriction	complete restriction of drinking
drinking	
_____	
9. Difficulty swallowing because of mouth* sores	
not difficult to	impossible to swallow
swallow	
_____	
10. Change in taste	
no change in	complete change in taste
taste	

### 13. Participant timeline

Enrolled patients will be divided randomly into two groups, each consists of 33patients.

**Intervention group:** Patients will receive mixture of Mebo and pumpkin seed oil spray three times daily

**Control Group:** Patients will receive Benzydamine Hydrochloride spray three times daily

**Follow up:** The patients will be recalled at one week interval for 14 days.

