## **I. Introduction**

### **1. Background and rationale:**

#### **Research question:**

In patients with oral mucositis, will MEBO result in clinical improvement as compared to Benzydamine Hydrochloride spray?

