#### **PICO:**

Population [P]: patients with oral mucositis attending the National Cancer Institute clinic

Intervention [I]: MEBO

Comparison [C]: Benzydamine Hydrochloride spray

Outcome [o]: clinical improvement and quality of life

Outcome measure		Method of measurement	Unit of measurement
1 ry Outcome	Clinical improvement	World Health Organization (WHO)scale.(1)  Oral Mucositis Assessment Scale (OMAS).(2)	Ordinal
2 ry Outcome	quality of life	Patient-Reported Oral Mucositis( PROMS scale).(3)	Continuous outcome (Score codes).

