#### **Rationale for conducting the research:**

Oral mucositis consequences can range from pain, decreased oral intake, impaired speech and swallowing to adverse events as severe as septicemia, increased hospitalization, and G-tube feeding (6)

A wide variety of agents have been tested to prevent OM or reduce its severity.(7) This trial will assess the usefulness of MEBO versus Benzylamine Hydrochloride mouth wash in management of oral mucositis in patients receiving radiotherapy and/or chemotherapy.

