## **7. Objectives**

### **Aim of the study:**

To assess the effect of MEBO versus Benzylamine Hydrochloride spray regarding clinical improvement of oral mucositis and quality of life of patients receiving radiotherapy and/or chemotherapy

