### Application Form

#### Human Subjects

##### Kindly fulfill the following:

##### **Research title:**

Clinical Evaluation of MEBO Versus ~~Benzydamine~~ Hydrochloride In Management of Patients with radiotherapy induced Oral Mucositis: Randomized Clinical Trial

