##### **• Research Procedure in brief:**

A random sample of adult patients receiving radiotherapy or chemotherapy and having sign and symptoms of oral mucositis and this. Enrolled patients will be divided randomly into two groups, each consists of 21patients.

**Intervention group:** Patients will receive MEBO three times daily for two week

**Control Group:** Patients will receive ~~Benzydamine~~ Hydrochloride spray three times daily

**Follow up:** The patients will be recalled at one week interval for two week

as there is no treatment of oral mucositis available in Egyptian market

We will offer palliative treatment that will alleviate the pain of oral mucositis

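### The protocol describes the experimental product in three different ways, so a reader cannot tell which product the trial tests

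*Combined protocol and SAP*

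**What the plan says.** Three places say what patients in the experimental arm will receive, and no two agree:

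- Section 11 (Interventions): "Patients will receive mixture of MEBO three times daily for 14 days". A mixture implies a second component, but none is named.
- Section 13 (Participant timeline): "Patients will receive mixture of Mebo and pumpkin seed oil spray three times daily". Here the second component is pumpkin seed oil.
- Application form, research procedure: "Patients will receive MEBO three times daily for two week". There is no mixture and no second component.

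The places that define the trial's purpose name MEBO with no second component, although none says that it is given alone. The research question asks "In patients with oral mucositis, will MEBO result in clinical improvement as compared to Benzydamine Hydrochloride spray". PICO lists "Intervention [I]: MEBO". The rationale says "This trial will assess the usefulness of MEBO versus" the comparator. The aim in section 7 begins "To assess the effect of MEBO versus Benzylamine Hydrochloride spray". The application form's title opens "Clinical Evaluation of MEBO Versus", and its objective follows the aim.

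Section 5 states that the protocol has a single version.

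**The concern.** A two-arm trial supports a conclusion about the product that was actually given, compared with the control. Here the aim is the effect of MEBO, yet both main-protocol sections that say what patients receive describe a mixture. A site following section 13 would give a combination, and the result could not answer the aim. A site following the application form would give MEBO and could answer it. The protocol does not let a reader tell which of these a reported result would describe.

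Other provisions depend on the same point:

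- Exclusion criterion 1, on allergy to the study treatment, can be applied fully only if the components are known.
- Adverse events are to be reported in relation to the administered drugs, which needs a defined product.
- The supplied ethics application describes MEBO only.

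**Working it through.** **Plan's own figure.** No figure in the plan depends on this point. For completeness, section 14 reproduces: a standardised effect of 1.011, 80% power and two-sided 5% alpha give 16.38 per group by the two-sample t-test, rounded up to the stated 17. Section 14 does not say which product that effect size belongs to, so it does not help to settle the question.

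**Possible readings.** The text fits at least four:

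| Reading | Where it comes from | What the between-arm contrast estimates |
|---|---|---|
| MEBO with nothing added | Application form; consistent with question, PICO, rationale and aim | MEBO versus benzydamine |
| One product containing MEBO and pumpkin seed oil | Section 13 | The combination versus benzydamine |
| MEBO plus a separate pumpkin seed oil spray | Section 13, if *spray* belongs to the oil only | The combination versus benzydamine |
| MEBO with another, unnamed component | Section 11 | An undefined combination versus benzydamine |

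Section 17 rules out masking because the treatments come in different forms. The control is a spray in sections 11 and 13. If *spray* in section 13 describes the mixture, both arms are sprays and section 17 conflicts with it. This weighs against reading section 13 as a single mixed spray but does not exclude it.

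**Identifiability if a component is added.** Let b be the mean in the benzydamine arm, M the difference MEBO minus benzydamine, and A the further effect of the added component.

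- Control mean: b
- Experimental mean: b + M + A
- Only available contrast: D = (b + M + A) − b = M + A

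This is one equation in two unknowns. Every pair with M + A = D fits the data equally well. For example, M = 0 with A = D fits, and so does M = −D with A = 2D, where MEBO's effect has the opposite sign to the observed difference. More patients sharpen D but do not separate M from A. If MEBO is given with nothing added, A = 0 and M = D.

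**Is the mixture wording left over from another document?** The supplied text cites references 1 to 14 and then 19. Items 15, 16, 17 and 18 are uncited by number, which is 4 of 19. Items 16 and 17 concern pumpkin seed oil, and item 15 a calf hemodialysate. Apart from section 13 and those two reference titles, pumpkin seed oil is never mentioned. The protocol's title, on metformin for oral leukoplakia, belongs to a different trial. This pattern suggests reused text. It does not prove it, because some pages were not available to this review.

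**The case against.** The strongest reply is that the conflict is narrower than three descriptions suggest. The wording in section 11 may be a fragment of the sentence in section 13, which leaves a choice between MEBO and MEBO with pumpkin seed oil. The mixture wording is probably left over, and if MEBO is given with nothing added there is no error in the estimate. The application form is a separate document, so the single-version statement does not rule out its having been drafted at another time.

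The citation evidence is also imperfect. The Quality of life section cites item 19 for the visual analogue scales, but item 19 is a coffee-and-honey trial. Item 18, on a patient-reported mucositis questionnaire, fits better. The uncited count therefore holds by printed number only. In addition, citations 15 to 18 would be expected between the Background and Quality of life sections, and no text is missing there, which strengthens the leftover-text explanation.

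Much of this is fair as a matter of degree. The harm is conditional, and the citation count is only circumstantial evidence. It does not remove the contradiction. Setting the application form aside, the protocol's question, PICO, rationale and aim still conflict with section 13 inside one version. Leftover wording that stands in the current protocol is still what the protocol specifies. If section 11 is a truncated form of section 13, then both delivery sections specify a combination that the aim does not mention.

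**Conclusion.** The concern holds. The plan contradicts itself on the identity of the experimental product, and the documents do not settle which product is intended. It must be fixed because the product under test determines what any result means.

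The extent is the whole experimental arm: 33 patients by sections 11 and 13, or 21 by the application form. The effect on the estimate is all or nothing in kind. With MEBO alone there is no error. With any component added in that arm only, MEBO's effect is not identifiable. No size or direction can be given, because the documents report no effect for an added component.

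The conclusion assumes that any added component is absent from the control arm, as all descriptions of that arm indicate.

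**What to change.** The sponsor should reconcile the research question, PICO, rationale, section 7, section 11, section 13 and the application form's title, objective and procedure into one statement of the components and form of the product in each arm. Section 17 should be checked against that statement. Stating the form for both arms is worthwhile because the rationale calls the comparator a mouthwash where sections 11 and 13 call it a spray. This review does not say which product is right.

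If dosing has occurred, the statement must come from treatment records, since an amendment cannot change what was given. The documents do not state trial status. Recruitment was to start in January 2022 with enrolment over one year, and the submission date is 12/9/2025, so dosing may already have taken place.

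In every case the conclusion should be limited to the product actually given. If that was a combination:

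1. Date the change to the aim and report it as a change from the stated objective, through the registry update described under Protocol amendments, not as a wording correction.
2. Check that the ethics application covers the added component.
3. Check that exclusion criterion 1 was applied to every component.

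The cost is small, with no extra patients or visits. Before dosing it is one amendment. After dosing it is a check of treatment records and, for a combination, the reported change of objective and the two further checks.
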